## **Statistical Analysis Plan**

**Specific Aim 1:** Repeated measures analysis of variance (ANOVA) will be used to assess differences between intervention and control groups on outcomes variables over time. Post-hoc analysis will be based on Fisher's least significant difference procedure for pairwise comparisons. Baseline comparisons between those who dropped out and those who completed all three waves of data collection will be determined using two-sample t-tests or chi-square tests, and the rate of retention will be compared between the two treatment arms using the chi-square test of association to assess whether differential drop-out occurred.

**Specific Aim 2:** Kaplan-Myer survival analysis with a logrank test will be used to make an overall comparison between time to rehospitalization or death event between intervention and control groups. Cox proportional hazards model will be used to estimate the hazard ratio of intervention effect on the prediction of the end-point of rehospitalization or death compared to usual care group, while controlling potential compounding factors.

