A two-group, randomized controlled design will be used to determine the effect of Family SWaP on sodium intake of patients with HF and family caregivers (Figure 1). Dyads will be randomly assigned to intervention or usual care group using a stratified randomization strategy after we determine patients' adherence level to SRD at baseline. Because adherence level at the baseline may affect outcomes, stratification is needed to insure similar sample characteristics between Family SWaP and usual care groups. Non-adherence will be defined as a 24-hour urinary sodium excretion greater than 3000 mg. The 3000 mg 24-hour urinary sodium excretion cut point was chosen because it is the upper limit of sodium intake recommended for patients with HF. The intervention will be delivered to both adherent and non-adherent patients because it has not known whether the intervention delivered to a dyad can maximize their adherence behavior or promote long-term adherence behavior. The intervention will be delivered 16 weeks (6 weekly 45 minutes sessions and 5 bi-weekly 20 minutes sessions).using video conferencing technology via digital device (i.e., ipad). Post-intervention effects will be assessed at 4 and 12 months to identify short- term and long-term post-intervention. We will collect hospitalization information up to 12 months by phone follow up. Dependent variables include adherence to the SRD, symptom distress, knowledge of SRD, perceived control, perceived social support, quality of life, and caregiving burden (caregiver only), symptom distress (patient only), and rehospitalization (patient only). We will also collect 4 variables to evaluate salt taste: salt food preference, sensory density, and diet quality. Qualitative data regarding salt taste preference and family experiences.

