After eligible patient-caregiver dyads sign the consent forms, they will participant in this study. Baseline data will be collected during a home visit. At the baseline assessment, they will fill out questionnaires using the RedCap system and collect 24-hour urine specimens. Urine containers, collection devices (urinals for men and toilet "hats" for women) and written instructions will be provided. The research assistant will interview participants to obtain demographic characteristics and to confirm their comorbidities. Information about demographics and comorbidities will be obtained using a structured questionnaire in interview. A research assistant and the dyads will set up the starting day of urine collection within 3 days of completion of questionnaires and pick up dyad's urine specimens in the dyad's home and deliver University of Kentucky Chandler Hospital Laboratory to determine 24-hour urinary sodium excretion level. Additional data collection for qualitative data, and diet quality will be also collected by home visiting. The medical chart will be reviewed to confirm only patients' comorbidities. After patients are categorized as adherent or non- adherent using 3000mg urine sodium cut point, the dyads will be randomly assigned to the Family SWaP intervention or usual care group using stratified randomization. Caregivers' adherence level at baseline will not be used in randomization but will be used to compare adherence at follow up. Dyads in the Family SWaP intervention will participate in a 16-week intervention delivered by the interventionist. The usual care patients will receive the standard medical and nursing care for HF patients provided at the clinics from which they were recruited. The usual care dyads will participate in the same data collection procedures as dyads in the intervention group. Follow-up data collection will be conducted 4 and 12 months after the intervention group completes the 16 week intervention to evaluate short and long term effects. At each follow-up, patient-caregiver dyads will complete the same questionnaires as baseline. Self-report of all hospitalization events will be collected from patients/family caregiver via monthly phone calls and a hospitalization logbook kept by the dyad for 12months. The medical record and administrative database will be queried to confirm rehospitalizations by the research nurse who will be blinded to the study group assignment. Data from the optional recorded interviews will be transcribed by a HIPAA compliant third party transcription service (REV).

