If research has the potential to identify individual results or discover incidental findings that could affect the health of a subject, describe plans to assess, manage, and if applicable disclose findings with individual subjects or provide justification for not disclosing. For IRB expectations, refer to the UK IRB "Frequently Asked Questions (FAQs) on the Return of Research Results or Incidental Research Findings" [\[PDF\]](#).

Demographic data, clinical characteristic information, and psychological and quality of life information will be obtained from brief interview of participants, medical record review using structured questionnaires. Adherence to diet will be assessed using 24-hour urine specimen. The 24-hour urinary sodium level will be determined at the University of Kentucky Medical Laboratory. Diet quality will be assessed using a structured online questionnaire. Qualitative data will be obtained through a structured questionnaire. Demographic data, lab results, history, other study related records and questionnaire responses will be kept confidential and de-identified for data purposes. A secure master list of names and research subject numbers will be kept in a password protected electronic file in a locked research office with access limited to research staffs who are listed in the study personnel list.

**Confidentiality:** Specify where the data/specimens will be stored and how the researcher will protect both the data and/or specimens with respect to privacy and confidentiality. Address physical security measures (e.g., locked facility, limited access); data security (e.g., password-protection, data encryption); safeguards to protect identifiable research information (e.g., coding, links, certificate of confidentiality); and procedures employed when sharing material or data, (e.g., honest broker (if applicable), written agreement with recipient not to re-identify). If you plan to procure, store, and/or share material (tissue/specimens/data) expressly for use in current or future research, describe measures that you will take to secure and safeguard confidentiality and privacy.

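### The Aim 1 repeated measures ANOVA adjusts for neither the outcome's baseline value nor the randomization stratum, which costs power unless the waves are highly correlated

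*Combined protocol and SAP*

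**What the plan says.** The Aim 1 paragraph of the SAP opens with this sentence: "Repeated measures analysis of variance (ANOVA) will be used to assess differences between intervention and control groups on outcomes variables over time". Pairwise comparisons then follow by Fisher's LSD. No covariate is listed, and the text does not say whether group-by-time or the group main effect is the test. Covariate control is mentioned only for the Aim 2 Cox model, without a list of factors.

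Research Description, Study Design: "Because adherence level at the baseline may affect outcomes, stratification is needed to insure similar sample characteristics". The stratum is defined on the patient's urine: "Non-adherence will be defined as a 24-hour urinary sodium excretion greater than 3000 mg". Follow-up is fixed by "Post-intervention effects will be assessed at 4 and 12 months".

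Research Procedures: once patients are classified at the 3000 mg cut, "the dyads will be randomly assigned to the Family SWaP intervention or usual care group using stratified randomization". For the questionnaire outcomes, "At each follow-up, patient-caregiver dyads will complete the same questionnaires as baseline". Of caregivers it says that their "adherence level at baseline will not be used in randomization but will be used to compare adherence at follow up", with no method given.

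Research Materials, Records and Privacy: "Adherence to diet will be assessed using 24-hour urine specimen".

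**The concern.** The stratifying variable is a dichotomized baseline value of the diet adherence outcome, and the questionnaire outcomes also have their own baseline values. The protocol states that baseline adherence may be prognostic and uses it to allocate, but the Aim 1 analysis does not carry it forward. The protocol's intention to use caregivers' baseline adherence has no counterpart in the SAP either.

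Treating baseline as a wave in a group-by-time test amounts to a change-score comparison. It subtracts the whole baseline value when only the part predicted by the correlation should be removed, and so adds noise unless that correlation is high. What is at stake is power, and a test term left to be chosen later. Validity is not at stake, because randomization protects the estimate.

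**Working it through.** **Inputs from the documents.** 300 dyads (Study Population); three waves (SAP, Aim 1); a stratum formed by cutting patient baseline sodium at 3000 mg (Study Design). The supplied text gives no alpha, power, effect size, SD, correlation or dropout, so the 300 cannot be reproduced.

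**Assumptions.** 150 per arm, two-sided 5% test, SD 1, compound symmetry with correlation r, complete data, effect 0.30 SD at both follow-ups. The blocked simulations also assume 50% non-adherent patients and blocks of 4 within strata.

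**Closed form, allocation not blocked.**

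- Planned group-by-time F. Effects by wave are (0, 0.3, 0.3), with mean 0.2. Squared deviations sum to 0.04 + 0.01 + 0.01 = 0.06. Noncentrality = (150/2) × 0.06/(1−r) = 4.5/(1−r), on 2 and 596 df.
- Test of arm at both follow-ups, given baseline. The follow-ups then have variance 1−r² and covariance r−r², so an equal effect at both meets the eigenvalue (1−r²)+(r−r²) = (1−r)(1+2r). Noncentrality = 75 × 2 × 0.09/((1−r)(1+2r)) = 13.5/((1−r)(1+2r)), on 2 and 296 df.
- Ratio = 3/(1+2r).

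| r | Noncentrality, planned | Noncentrality, adjusted | Ratio | Power, planned | Power, adjusted |
|---|---|---|---|---|---|
| 0.3 | 6.43 | 12.05 | 1.88 | 61% | 88% |
| 0.4 | 7.50 | 12.50 | 1.67 | 69% | 89% |
| 0.5 | 9.00 | 13.50 | 1.50 | 77% | 92% |
| 0.6 | 11.25 | 15.34 | 1.36 | 86% | 95% |
| 0.7 | 15.00 | 18.75 | 1.25 | 94% | 98% |
| 0.8 | 22.50 | 25.96 | 1.15 | 99% | 99.7% |

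Inverting the ratio, 300 dyads analyzed as planned are worth 300 × (1+2r)/3 = 160, 200 and 240 baseline-adjusted dyads at r = 0.3, 0.5 and 0.7.

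**Waning effect (0.30, then 0.15 SD).** Planned against adjusted: 49 vs 71, 55 vs 74, 64 vs 78, 74 vs 84, 86 vs 91 and 97 vs 98% at r = 0.3 to 0.8.

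**Patient sodium, simulated with blocking within strata.**

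| r | Planned F | Planned F + stratum | Baseline-adjusted | Gain, adjusted − planned (points) |
|---|---|---|---|---|
| 0.3 | 62.5% | 71.3% | 87.7% | 25.2 |
| 0.4 | 70.3% | 76.5% | 88.8% | 18.5 |
| 0.5 | 79.2% | 83.6% | 91.3% | 12.1 |
| 0.6 | 88.4% | 90.4% | 94.8% | 6.4 |
| 0.7 | 95.6% | 96.4% | 98.0% | 2.4 |
| 0.8 | 99.6% | 99.7% | 99.8% | 0.2 |

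The planned F is somewhat conservative here, with simulated size 3.2 to 4.3%. Adding the stratum restores 4.9 to 5.6%. Without blocking its size is 4.4 to 5.3%. Once the continuous baseline is in the model, the stratum changes power by at most 0.3 point.

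**Other outcomes (baseline correlation with sodium 0 or 0.3).** Size is 4.5 to 5.6%. Adding the stratum to the planned F gains under 1 point. Adjusting for the outcome's own baseline gains 26–28, 14–15, 8, 3–4 and under 1 points at r = 0.3, 0.5, 0.6, 0.7 and 0.8.

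**If the group main effect over three waves is meant.** The pre-randomization wave dilutes the effect to two thirds. Simulated power for patient sodium falls from 68.6% at r = 0.3 to 44.0% at r = 0.8, against 93.5 to 99.9% for the baseline-adjusted mean of the two follow-ups.

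**Cross-check with a different contrast and scaling.** Set the effect so that the baseline-adjusted mean of both follow-ups has 80% power. The matching 1-df group-by-time contrast then has 53, 63, 71 and 77% at r = 0.3, 0.5, 0.7 and 0.9. The pattern does not depend on the choice of 0.30 SD.

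**The case against.** The strongest reply is that this is a question of efficiency only. A repeated measures ANOVA with baseline as a wave is a valid test in a randomized trial, it does not inflate false positives, and under the assumptions above it already reaches 77% power or more from r = 0.5 upward. The large gains appear only at r of 0.3 to 0.4, and the documents do not say where r lies. All of that stands, and it limits the point to a recommended improvement.

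The stratum itself contributes little: almost nothing once the continuous baseline is included, and under 1 point for other outcomes. That also stands. The gain is mainly ordinary ANCOVA efficiency; the stratum belongs in the model to match the design.

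High correlation removes the loss only under the group-by-time reading. That is the natural reading of a comparison over time, but the SAP does not commit to it, and under a main-effect reading high correlation makes matters worse. The ambiguity is a reason to name the term.

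Two limits of the text also apply. Study Population refers to a data analysis section that is not in the supplied material and might say more. The follow-up sentence in Research Procedures covers questionnaires; repeat urine collection is inferred from adherence being a dependent variable assessed by 24-hour urine. Neither changes what the current SAP wording says.

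**Conclusion.** The concern holds as a SHOULD-level point, with medium confidence. The Aim 1 text names no covariate, although each outcome's baseline value and the stratum are available before randomization. Under the group-by-time reading, the closed-form loss is about 27 points at r = 0.3 (88 − 61), 15 at 0.5 (92 − 77) and 4 at 0.7 (98 − 94), and under 1 point at 0.8. These sizes rest on the assumed correlation structure, effect, allocation and complete data; the direction and the efficiency ratio 3/(1+2r) need only compound symmetry and an equal effect at both follow-ups. Conservatism of the planned test applies to patient sodium alone, and only if allocation is balanced within strata, which the protocol does not state.

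**What to change.** In Aim 1, model the 4- and 12-month values jointly, with the same outcome's baseline value (continuous) and the patient adherence stratum as covariates, and report the arm difference at each time. For caregiver sodium, use the caregiver's own baseline sodium, which also gives effect to the statement in Research Procedures. State which term is the test: arm at both follow-ups jointly, or the mean of the two.

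As a minor matter of consistency, stratify the Aim 2 log-rank test and Cox model by patient baseline adherence. The log-rank gain is small: about 0.5 to 2 points at an assumed stratum hazard ratio of 1.5 to 2, and 3 to 5 points only near 3 (assuming a treatment hazard ratio of 0.65, 30 to 50% with an event by 12 months and 150 patients per stratum).

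The cost is SAP wording only. No new data, visits or participants are needed. The change should be made before outcomes are compared by arm.

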There is no monetary incentive to compensate for their time during 12 months. However, each dyad (patients and their family caregiver dyad) who participant in this study will receive an iPad per family at the beginning of the study. If any one of the dyad members withdraws the study before three assessments complete, we consider patient-caregiver dyad as a unit of the study will end the study and they should return the iPad that will be given during the study. When two dyad members complete all three assessments during 12 months study, the dyad will keep the iPad. Free data plan will be provided for only dyads that don't have home Wi-Fi access during the study (12 months).

**Costs to Subjects:** Describe any costs for care associated with research (including a breakdown of standard of care procedures versus research procedures), costs of test drugs or devices, and research procedure costs that are the subject's responsibility as a consequence of participating in the research. Describe any offer for reimbursement of costs by the sponsor for research related injury care.

There will be no additional costs to the participants and no personal travel costs to the research site.

**Data and Safety Monitoring:** The IRB requires review and approval of data and safety monitoring plans for greater than minimal risk research, clinical research, or NIH-funded/FDA-regulated clinical investigations.

If you are conducting greater than minimal risk research, clinical research, or your clinical investigation is NIH-funded/FDA-regulated, describe your Data and Safety Monitoring Plan (DSMP). [Click here for additional guidance on developing a Data and Safety Monitoring Plan.](#)

If this is a *non-sponsored investigator-initiated* protocol considered greater than minimal risk research, clinical research, or your clinical investigation is FDA-regulated, *and* if you are planning on using a Data and Safety Monitoring Board (DSMB) as part of your

DSMP, [click here for additional guidance](#) for information to include with your IRB application.

If relying on an independent agent or committee for DSMB services, it is the PI's responsibility to establish the services with the agent or committee. Please be reminded that the PI must submit DSMB reports to the IRB via modification or continuing review. 

We have developed a detailed Data Safety Monitoring Plan that includes the following elements.

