- a. Periodic Review: The Principle Investigator (PI) will hold weekly staff meetings for the first month of enrollment then bi-weekly thereafter. The staff meeting will include the PI, co- investigators, project director, nurses in charge of recruitment and the intervention, and the data manager. The meeting will include evaluation of all research procedures, fidelity to protocol, discussion of newly enrolled participants, and review of status of all formally enrolled participants including all adverse events. Adverse events will be reviewed to determine if changes in the protocol are indicated. Participant demographics to date, recruitment progress, and difficulties encountered during enrollment, an update on data entry, and any other issues or concerns that have arisen since the last research team meeting will also be discussed.
- b. Adverse Events: The educational intervention study is minimal risk. We do not anticipate moderate, severe, life-threatening or fatal AEs. Regardless, adverse events will be defined in accordance with Federal Regulation 21CFR §56.108(b)(1) and 45 CFR 46.103(b)(5). Adverse events that are unexpected and related to the study will be promptly reported to the University Institutional Review Board (IRB). The Data and Safety Monitoring Plan for the proposed project incorporates the policies on human subject data and safety monitoring specified by the University of Kentucky IRB.
- c. Plan for Safety Review: A methodical review of all procedures will be an integral part of each research team meeting. Review will include discussion of protocol to ensure adherence, discussion of procedures to insure confidentiality is maintained and that data are collected with minimal risk for violations of confidentiality. A meeting involving the PI, co- investigators, and research nurses will be called if an unexpected adverse event occurs.
- d. Plan for Data Quality: The research design, methods and procedures will be reviewed by all members of the research team during staff meetings. Meetings with PI and data manager will be conducted every 3 months to verify accuracy of data entry, identify missing data, and run preliminary analyses of demographic, to verify enrollment targets, and outcomes. Data entry errors will be corrected and plans will be developed to address any systematic problems related to data entry and integrity.

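### Aim 1 rests on repeated-measures ANOVA with no rule for missing waves; run conventionally, it discards first follow-up values already measured, which costs precision and can bias the short-term contrast

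*Combined protocol and SAP*

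**What the plan says.** The Statistical Analysis Plan, Specific Aim 1, states: "Repeated measures analysis of variance (ANOVA) will be used to assess differences between intervention and control groups on outcomes variables over time". Fisher's least significant difference follows for pairwise comparisons. The Cox model belongs to Aim 2.

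Dropout appears in Aim 1 in two comparisons only:

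- A check of baseline differences: "Baseline comparisons between those who dropped out and those who completed all three waves of data collection will be determined using two-sample t-tests". The plan names the chi-square test as the alternative to the t-test here.
- A check of attrition by arm: "the rate of retention will be compared between the two treatment arms using the chi-square test of association to assess whether differential drop-out occurred".

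Neither has a stated consequence for the analysis.

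Elsewhere:

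- **Study Design** makes the first follow-up the short-term estimate: "Post-intervention effects will be assessed at 4 and 12 months to identify short- term and long-term post-intervention". **Research Procedures** adds: "At each follow-up, patient-caregiver dyads will complete the same questionnaires as baseline".
- **Data and Safety Monitoring**, item d, has data meetings "every 3 months to verify accuracy of data entry, identify missing data, and run preliminary analyses". That is a data-quality step, not an analysis rule.
- **Payment** contains a garbled sentence about withdrawal by a single member: "the dyad members withdraws the study before three assessments complete, we consider patient-caregiver dyad as a unit of the study will end the study". A caregiver's withdrawal can therefore remove the patient's later waves.
- **Specific Aim 2** expects deaths: "Kaplan-Myer survival analysis with a logrank test will be used to make an overall comparison between time to rehospitalization or death event".
- **Study Population** points to a sample size justification in a data analysis section that is not in the supplied text, so a missing-data rule could sit there.

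**The concern.** The dropout comparisons separate completers of all three waves from the rest, so partial records are expected, yet nothing says how they are analysed. Listwise deletion is not written in the plan. It is what a conventional repeated-measures ANOVA does: one missing wave removes the whole person.

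Two things are at stake.

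- **Precision of the short-term contrast.** Measured values go unused. This happens whatever the reason for dropout, provided some loss falls after the first follow-up.
- **Bias in the same contrast.** This arises if later dropout depends on the first follow-up value differently by arm. The two planned dropout comparisons describe attrition but do not protect the estimate.

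**Working it through.** **Inputs.** From the documents: 300 dyads and three waves. Assumed, because the documents do not give them: 1:1 allocation (150 per arm), dropout of 10 to 30%, its timing and mechanism, and the within-person correlations. The 300 itself cannot be reproduced, because no effect size, SD, alpha, power or dropout rate is in the supplied text.

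**Step 1. Precision at the first follow-up, random loss d per arm.** The ratio of the completers' SE to the SE with all observed values is:

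- all loss after the first follow-up: 1/√(1−d)
- half of it after: √((1−d/2)/(1−d))
- constant dropout rate over follow-up: √((1−d)^f/(1−d)), where f is the share of follow-up elapsed at the first visit. Study Design gives f = 4/12. Research Procedures counts from the end of the 16 weeks; taking these as 4 months, f = 8/16.

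| Loss d | Completers per arm | First follow-up values discarded, all late | SE increase, all late | Half late | Constant rate, f = 1/3 | Constant rate, f = 1/2 |
|---|---|---|---|---|---|---|
| 10% | 135 | 30 | 5.4% | 2.7% | 3.6% | 2.7% |
| 20% | 120 | 60 | 11.8% | 6.1% | 7.7% | 5.7% |
| 30% | 105 | 90 | 19.5% | 10.2% | 12.6% | 9.3% |

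Example: at 20% all late, 1/√0.8 = 1.118; half late, √(0.9/0.8) = 1.061.

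**Step 2. Power.** The difference with 80% power at 150 per arm is (1.960 + 0.842) × √(2/150) = 0.323 SD. At 135, 120 and 105 per arm, power for it is 75.7%, 70.7% and 65.0%. With 20% loss all late, completers-only analysis therefore gives 70.7% where all observed values give 80%. With half the loss late, it is 70.7% against 75.7%.

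**Step 3. Simulation.** Settings: 150 per arm; correlations of 0.3 or 0.5 at all lags, or a decaying pattern (0.4/0.3/0.6). The completers' group-by-time F-test was compared with maximum likelihood on all observed waves, with 2,500 to 4,000 trials per setting. With 4,000 trials, Monte Carlo error near 5% is about ±0.7 points.

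*Random 20% loss after the first follow-up:* the completers' SE was 11 to 13% larger at the first follow-up and 4 to 6% larger at 12 months. Group-by-time power for a true 0.30 SD was 49.3/66.9/56.7% for completers and 58.6/75.8/58.7% for likelihood (correlation 0.3/0.5/decaying). At 10% loss with decaying correlations the ANOVA was not less powerful (61.9% against 59.0%).

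*No true effect, dropout depending on the first follow-up value in one arm only, equal retention:*

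| Loss | Log-odds per SD | Completers' bias (SD) | Completers' false positives |
|---|---|---|---|
| 10% | 0.3 | 0.01–0.02 | 4.9–5.4% |
| 10% | 0.7–1.0 | 0.03–0.07 | 5.3–7.2% |
| 20% | 0.3 | 0.03–0.04 | 5.4–6.3% |
| 20% | 0.5 | 0.05–0.07 | 6.5–7.3% |
| 20% | 0.7–1.0 | 0.06–0.12 | 7.4–12.0% |
| 30% | 0.3 | about 0.05 | 6.6–7.3% |
| 30% | 0.7–1.0 | 0.10–0.18 | 10–19% |

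In the 20% settings, likelihood bias was 0.004 SD or less, with 4.7 to 5.5% false positives. The completers' 12-month bias was 0.005 SD or less with equal correlations and 0.011 to 0.036 SD with decaying ones.

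*Same mechanism in both arms, 20%:* no bias without a true effect. With a true 0.30 SD, the pull toward zero was 0.005 SD or less at log-odds 0.3 and 0.012 to 0.022 SD at 0.7 to 1.0.

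*Separate simulation, true effect −0.30 SD, log-odds 1.0:* with 20% loss in each arm and dependence in one arm only, the completers' first follow-up estimate was −0.42, −0.39 and −0.35 at correlations 0.3, 0.5 and 0.7. With the same dependence in both arms but 10% against 30% loss, it was −0.41, −0.38 and −0.35. The all-data fit stayed between −0.295 and −0.303.

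**Step 4. Would the planned checks catch it?** Under the one-arm mechanism at 20%, the retention chi-square rejects in 5 to 6% of trials. The baseline comparison rejects in 6 to 9% (log-odds 0.3) or 10 to 33% (0.7 to 1.0). When both pass, false positives remain 5.2 to 6.3% and 7.3 to 11.9%.

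**Step 5. Dyad rule.** If members leave independently, individual withdrawal of 5%, 10% or 15% loses 1 − 0.95² = 9.8%, 1 − 0.90² = 19.0% or 1 − 0.85² = 27.8% of dyads. If they always leave together, the dyad rate equals the member rate.

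**The case against.** The strongest case against has four parts.

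- **Deletion is inferred.** The plan's label does not fix an estimation method, and a rule may sit in the unsupplied data analysis section. This stands as a limit. However, the text headed Statistical Analysis Plan is supplied, discusses dropout, and gives no rule.
- **The precision cost needs late loss.** This stands. The 11.8% is the upper end at 20% loss. A constant dropout rate on the plan's own visit times gives about 3 to 8% at 10 to 20% loss. If all loss precedes the first follow-up there is almost nothing to recover (2 to 4% in simulation, with value-dependent loss).
- **The bias scenarios are assumed.** This stands. At log-odds 0.3 and 20% loss, false positives of 5.4 to 6.3% lie within the 4.4 to 6.4% that completers show under random or shared dropout, and a repeat run gave 5.1 to 5.8%. Clear inflation needs stronger, arm-specific dependence, for which the documents offer no evidence. The iPad, home data collection and monthly calls all favour retention.
- **The mixed model can be worse.** This also stands. The arms differ most during the 16-week intervention, before the first follow-up. Take 20% loss and log-odds 0.7 to 1.0 in one arm. If dropout is early or depends on the unseen 12-month value, mixed-model bias in the affected contrast is 0.08 to 0.16 SD against 0.06 to 0.12 SD for completers. False positives are 9.4 to 17.7% against 7.2 to 13.2%. At log-odds 0.3, bias is 0.04 to 0.06 against 0.03 to 0.05 SD, and false positives are 5.8 to 7.4% against 5.2 to 6.7%.

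These points limit the size of the problem and make a sensitivity analysis necessary. They do not supply the missing rule or give a reason to discard measured values.

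**Conclusion.** The concern holds and should be fixed. The gap in the supplied text is plain, and the precision loss is arithmetic once some dropout falls after the first follow-up. At 20% random loss the SE cost runs from almost nothing (all early) through about 6 to 8% (half late, or a constant rate) to 11.8% (all late).

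Bias in the short-term contrast is possible but conditional: 0.03 to 0.12 SD at 20% loss under one-arm, value-dependent dropout, and none under random dropout. With the same mechanism in both arms there is none without a true effect and at most 0.022 SD toward zero with one. The 12-month contrast is little affected by this mechanism.

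Confidence in the size is medium, because dropout rate, timing, mechanism and correlations are all assumed.

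**What to change.** Replace the Aim 1 ANOVA with a likelihood-based mixed model for repeated measures. If such a fit was already intended, say so. The SAP should state:

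1. All randomised dyads are analysed as assigned, using every observed wave, with arm by categorical time and an arm contrast at each follow-up.
2. Patients and caregivers are modelled separately, or together with a dyad-level term.
3. How Aim 1 waves missing because of death are treated.
4. A not-at-random sensitivity analysis, with the range of departures fixed in advance.
5. The two dropout comparisons are kept as description, shown by arm.

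The covariance structure and the form of the sensitivity analysis are the statistician's choice. The visit timing also needs reconciling: Study Design gives 4 and 12 months, while Research Procedures counts the same intervals from the end of the 16-week intervention.

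The cost is SAP wording and a little more programming, with no extra data, visits or participants. The downside is the greater bias of the mixed model under early or unseen-value dropout, so item 4 should not be omitted.
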